- Subjects who are treatment crossovers (non-overminus group subjects who are prescribed overminus therapy; overminus group subjects who have overminus spectacles formally discontinued) will have their observed 12-month data analyzed provided they complete at least one distance control testing at the 12-month outcome exam; otherwise their average distance control score will be imputed using multiple imputation.
- Subjects who are prescribed IXT treatment *other than overminus or non-overminus refractive correction* (e.g. surgery, vision therapy, patching) will have their average distance control score imputed using multiple imputation, using data from all visits prior to the initiation of the alternative therapy. Multiple imputation will be used for these subjects regardless of whether any control testing is completed at the 12-month visit.
- Subjects who are lost to follow up before the 12-month visit will also have their outcome imputed using multiple imputation.

The original primary analysis is now an alternative analysis in section 5.1.1.1, along with the original alternative analysis. A third alternative analysis has been added to explore the effect of how treatment crossovers are handled in the primary analysis.

The secondary 18-month off-treatment analysis was changed in parallel (section 5.2).

Rationale for Change

For subjects who are prescribed treatment other than what they were randomized to (e.g. surgery, overminus spectacles, vision therapy) the 12-month visit data would reflect the effect of the non-randomized treatment they receive. If a higher proportion of subjects in the non-overminus group are prescribed a non-randomized treatment that is more effective than the overminus spectacles, the study might fail to detect an effect of overminus, if one exists. It was felt acceptable and conservative to analyze the observed 12-month data for treatment crossovers given that these subjects are receiving study treatments; however, it was felt appropriate to impute 12-month data using multiple imputation for subjects who are prescribed IXT treatment other than overminus or non-overminus refractive correction (e.g. surgery, vision therapy,

patching), an approach which would not be expected to bias the analysis either toward or against a treatment effect of overminus (although any procedure for handling of this issue has some potential for bias). A similar rationale applies to the 18-month off-treatment analyses.

413 414

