3.6 Additional Visits

1470 Investigators may schedule additional visits at their own discretion.

If the investigator plans to initiate non-randomized treatment for IXT at an additional visit, a masked examination (following all testing procedures in *section 3.4* except for the cycloplegic

refraction / autorefraction) must be performed prior to initiating the new treatment. If a masked examiner is unavailable, data from an unmasked exam should be entered on the website, noting that the examiner was unmasked. If the investigator is starting non-randomized treatment, the subject does not return for a stereoacuity retest if stereoacuity is decreased (section 3.7).

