102
103
104
105
106
107
108
109
110
111
112
113
114

The 12-month distance control score for analysis for each participant is the mean of the 3 control assessments completed at that visit. When the protocol-specified three measures of control are not performed at the outcome exam, the mean of two measures will be used for analysis if only 2 distance control measures are completed; the single distance control score will be used for analysis if only 1 assessment of control is completed.

The primary analysis will follow a modified intention-to-treat principle, with all participants analyzed according to their randomized treatment group and with the following stipulations:

- Participants who are treatment crossovers (non-overminus group participants who are prescribed overminus; overminus group participants who have overminus spectacles formally discontinued before 12 months) will have their observed 12-month data analyzed provided they complete at least one distance control assessment at the 12-month outcome exam; otherwise, their mean distance control score will be imputed using multiple imputation.
- Participants who are prescribed IXT treatment other than overminus or non-overminus spectacles (e.g., surgery, vision therapy, patching) will have their mean distance control score imputed using multiple imputation, regardless of whether any control testing is completed at the 12-month visit.
- Participants who miss the 12-month visit or who do not complete any control testing at the 12-month visit, including treatment crossovers who miss or do not complete the 12-month visit, will also have their mean distance control score imputed using multiple imputation.
- To be included in the analysis, the 12-month visit must be completed no earlier than 270 days (≥ 9 months) and no later than 540 days (≤ 18 months) after randomization. If the 12-month visit is not completed within this analysis window, the distance control at 12-month visit will be imputed using multiple imputation.
- Data from participants randomized but found to be ineligible upon subsequent review of enrollment data will be included in the primary analysis.

The multiple imputation will be performed for missing data using Monte Carlo Markov Chain (MCMC) modeling. (See Section 2.4 below for further details.)

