2.1.3. Sensitivity Analysis #1: Complete Case Analysis (Excluding Out-of-Window Visits)

- The observed data (NOT the imputed dataset) will be used.
- All participants who complete one or more distance control assessments at a 12-month visit occurring between 9 to 18 months from randomization, including treatment crossovers and participants who are prescribed IXT treatment other than overminus or non-overminus spectacles, will have their observed 12-month data analyzed.
- Participants who miss the 12-month visit entirely or who do not complete any control testing at the 12-month visit will be excluded from the analysis.
- Participants who had the 12-month visit completed outside of the analysis window (<9 months or >18 months from randomization) will be excluded from the analysis.

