349 they were not included in version 1.0 of the protocol or SAP. Because using stereoacuity
350 as the (sole) outcome for IXT has ample precedent in the literature, an additional analysis
351 will be conducted using a post-hoc alternative definition of deterioration which classifies
352 the participant's condition as deteriorated only if the participant met stereo deterioration
353 criteria. *Unlike for the analysis of overall deterioration, participants with nil stereo at*
354 *baseline will be excluded from this analysis.* The analysis will be adjusted for baseline
355 near stereoacuity.

356
357

358 **4. Objective III: Other Clinical Outcomes, Exploratory Analyses, and Safety**

359 The analyses specified below will use the observed data and only the visits that occurred
360 within the analysis window will be included. For all outcomes, the data will be tabulated
361 and means and standard deviations, or proportions, will be calculated for each of the
362 treatment groups. The type I error rate for analyses of the secondary outcomes specified
363 in the sections below will be controlled using false discovery rate (FDR) to account for
364 the multiple outcomes. The outcomes will be divided into 2 groups for this purpose, with
365 FDR controlled at the 5% probability level within each group. The first group is
366 comprised of the clinical measures (no spontaneous tropia, near control, angle magnitude,
367 stereoacuity, axial length and other biometric measures, and refractive error) and the
368 second is comprised of the symptom and quality of life measures.

369

370 **4.1 Other Clinical Outcomes at 12 and 18 Months**

371

372 For the 18-month visit, all analyses will be repeated, limited to participants who were
373 prescribed weaning (i.e., prior to weaning being discontinued per Protocol Amendment
374 II). This will be done because if retention of an on-treatment effect is stronger in
375 participants who have full weaning vs. less than full weaning, the 18-month treatment
376 effect could be diluted in the full cohort analysis vs. the limited cohort.

377

378 **4.1.1 No Spontaneous Tropia**

379 The proportion of participants with no spontaneous tropia will be compared between the
380 two treatment groups using a two-sided Barnard's test (with alpha of 0.05) at 12 months
381 and 18 months. The difference in proportions, a two-sided 95% confidence interval, and
382 p-value on the difference in proportions will be calculated.

383

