485 “sometimes”, and “all the time.” The distribution for each individual item will be
486 tabulated for each treatment group for each outcome time point.

487

488 A 7-item survey consisting of IXT-related symptoms and problems with spectacle wear
489 will be completed by parents of participants at the enrollment, 6-month, 12-month, and
490 18-month exams. The parent is asked how often symptoms or problems occur, using the
491 response choices of “never,” “almost never,” “sometimes”, “often”, “almost always.” The
492 distribution for each individual item will be tabulated for each treatment group for each
493 outcome time point.

494

495 **4.1.12 Compliance with Spectacle Wear**

496 Compliance with spectacle wear will be assessed at the 6-month, 12-month, 15-month,
497 and 18-month exams. Parents will provide an estimate of the proportion of the time their
498 children wore their spectacles. Proportion of time worn will be described as excellent
499 (76% to 100%), good (51% to 75%), fair (26% to 50%), or poor ($\leq 25\%$). The
500 distribution of compliance will be tabulated for each treatment group for each time point.

501

502 **4.2 Exploratory Analyses**

503 The following exploratory analyses will use observed or imputed data (see LOCF,
504 below), as follows:

- 505 • All participants who complete one or more distance control assessments at a specific
506 visit within the corresponding analysis window, including treatment crossovers, will
507 have their observed data analyzed, except for participants who are prescribed non-
508 study treatment (i.e., IXT treatment other than overminus or non-overminus refractive
509 correction), who will have the distance control from the (first) visit when non-study
510 treatment was prescribed carried forward.
- 511 • Participants who miss the study visit entirely or who do not complete any control
512 assessments at the visit will be excluded from the analysis for that visit.
- 513 • Participants who had the visit completed outside of the analysis window will be
514 excluded from the analysis for the visit.

515

516 **4.2.1 Mean Distance Control in Baseline Subgroups**

517 The treatment group comparisons of 12-month distance control will be assessed in
518 subgroups based on baseline factors. Subgroup comparisons for 18-month distance
519 control will be explored only if there is an overall treatment group difference in distance

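### Four secondary outcomes use observed data after surgery, patching or vision therapy; this departs from the primary analysis without explanation, and no alternative handling is planned for them

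*SAP*

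**What the plan says.** SAP Section 4 sets one data rule for the outcomes below it: "The analyses specified below will use the observed data and only the visits that occurred" within the analysis window. Sections 4.1.1, 4.1.2, 4.1.5 and 4.1.6 add no exception for a child prescribed non-study treatment for intermittent exotropia.

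The meaning of observed data is clear from SAP 2.1.3 (Sensitivity Analysis #1). There "The observed data (NOT the imputed dataset) will be used", and "treatment crossovers and participants who are prescribed IXT treatment other than overminus or non-overminus spectacles, will have their observed 12-month data analyzed".

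The primary analysis does the opposite. Under SAP 2.1.1, those given any therapy beyond the two kinds of study "spectacles (e.g., surgery, vision therapy, patching) will have their mean distance control score imputed using multiple imputation, regardless": a completed 12-month test makes no difference. Protocol Amendment I, Change #3, gives the reason: for children prescribed something other than their randomised treatment, "the 12-month visit data would reflect the effect of the non-randomized treatment they receive". It adds that the study might then fail to detect a real overminus effect.

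SAP 4.2 (exploratory analyses) uses a third rule. It makes an explicit exception for children prescribed non-study treatment, "who will have the distance control from the (first) visit when non-study" treatment was prescribed, carried forward.

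**The concern.** The responder outcomes in 4.1.2 are built from the same distance control scores as the primary mean. The primary analysis sets aside a score obtained after surgery, and the responder analysis counts it. If the Amendment I reasoning holds for the mean, it should hold for a threshold on that mean, and the SAP does not say why it would not. PACT raises the same question, since the deviation is what surgery aims to change.

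These outcomes carry p-values. No spontaneous tropia, angle magnitude and stereoacuity belong to the first false-discovery-rate group in SAP Section 4. The improvement proportions are tested at 0.05. No spontaneous tropia also has its own power statement in Protocol 5.7.1 and 5.7.2.

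Rescue is not random. Protocol 3.7 and 3.8 allow it after deterioration or by approved exception. After deterioration the decision is at the discretion of the investigator, who at most sites knows the arm (Protocol 3.3). Follow-up continues after rescue, so the post-rescue data will exist.

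**Working it through.** **Step 1. Handling of a child prescribed surgery, patching or vision therapy**

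| Analysis | Handling |
|---|---|
| Mean distance control, 12 months (SAP 2.1.1, 2.1.9) | Imputed from visits before that treatment |
| Mean distance control, 18 months (SAP 2.2.1) | Same principle |
| Deterioration (SAP 3.1) | Censored 0.1 month after the prescribing visit |
| Exploratory distance control (SAP 4.2) | Score at the prescribing visit carried forward |
| Near control (SAP 4.1.4) | Follows Section 2, so imputed, against the Section 4 sentence |
| SAP 4.1.1, 4.1.2, 4.1.5, 4.1.6 | No rule, so the observed value is used |

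A concrete case: motor deterioration means a score of 5 on all three assessments at distance and near (Protocol 3.7). At that visit the child cannot meet no spontaneous tropia (2 or better on every assessment) and cannot have improved from baseline. If operated on successfully before 12 months, the child is an event in SAP 3.1, is imputed in the primary analysis, and is a success in 4.1.1 and possibly in 4.1.2.

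**Step 2. Reproduce the plan's figure**

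No spontaneous tropia is the only affected outcome with a stated power: 74% for a 15-point difference, N = 364 with 10% loss (Protocol 5.7.1). I use 163 per arm, the plan's evaluable number, and two-sided alpha 0.05. The base rate is not stated, so I assume 57.5% vs 42.5% (centred on 50%, the largest variance).

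Power = Φ{[(|p1 − p2| − 1/n) − 1.96 × √(2p̄(1 − p̄)/n)] / √([p1(1 − p1) + p2(1 − p2)]/n)}

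- 1/n = 1/163 = 0.0061, so the corrected difference is 0.1439.
- 1.96 × √(0.5/163) = 0.1086.
- Denominator = √(0.48875/163) = 0.0548.
- Power = Φ(0.0353/0.0548) = Φ(0.645) = 74.0%.

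The stated 74% reproduces; without the continuity correction the result is 77.5%. The confidence interval half-width is 1.96 × 0.0548 = 10.7 points, against the stated 11.

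**Step 3. Illustrate the possible size**

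The documents give neither a rescue rate nor a success rate after rescue. All rates here are assumptions. Let f_O and f_N be the proportions rescued in the overminus and non-overminus arms. Assume every rescued child would otherwise fail the outcome, and that a share s of 50% to 80% are classed as successes afterwards.

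Observed difference = 15 + s × (f_O − f_N), in percentage points.

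Example: f_O = 2%, f_N = 5%, s = 50% gives 15 + 0.5 × (−3) = 13.5.

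| f_O / f_N | Observed difference (s = 50% to 80%) | Power |
|---|---|---|
| 0% / 2% | 14.0 to 13.4 | 68% to 64% |
| 0% / 5% | 12.5 to 11.0 | 57% to 47% |
| 2% / 5% | 13.5 to 12.6 | 64% to 58% |
| 5% / 10% | 12.5 to 11.0 | 58% to 47% |
| 5% / 5% | 15.0 | 74% |
| 5% / 0% | 17.5 to 19.0 | 87% to 92% |

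Only the difference in rescue between arms moves the estimate. If rescued children were counted as failures, the difference would stay at 15 points under these assumptions.

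**The case against.** The strongest reply is that this is a valid and apparently deliberate treatment-policy comparison. The SAP revision history records that the imputed-data sentence for stereoacuity was removed because observed data would be used. Amendment I redefined the distance control analyses and set no rule for PACT or stereoacuity, and it concedes that any handling carries some risk of bias. Protocol 5.1.2 and 5.3 leave secondary details to the SAP. Sensitivity Analysis #1 supplies an observed-data mean to set beside the responder rates. Protocol 5.5 tabulates non-randomised treatment by arm, so readers can judge its extent. All of this stands, and it limits the point to an unexplained departure and a missing companion analysis. It does not supply that companion for the four outcomes: Sensitivity Analysis #1 covers mean control only.

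The numbers are also likely to be small. SAP 3.1 calls deterioration rates low in an earlier study, the criteria are strict, exceptions need the protocol chair's approval, and masked examiners do the protocol-visit testing.

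Carry-forward, as in SAP 4.2, is a poor remedy as the main rule. It freezes the child at a visit selected for poor results, while Protocol 1.13 gives a simulated test-retest standard deviation of 0.926 points. Protocol 3.6 says that a masked examination at an additional visit "must be performed prior to initiating the new treatment", but accepts an unmasked one if no masked examiner is available, and drops the later-day stereoacuity retest.

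A reader might infer that the observed-data results must credit surgery to the lens and so hide an overminus effect. The documents do not support that. It requires more rescue in the non-overminus arm, and no rate is given for either arm.

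**Conclusion.** The point holds as a gap in specification and consistency. The SAP text available for this review (part of 4.3 to 5.2 was not) handles non-study treatment explicitly in its other distance control and deterioration analyses. For these four outcomes it neither justifies observed data nor plans an alternative, despite the sponsor's stated reason for avoiding such data in the primary analysis.

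The distortion cannot be sized or signed from the documents and is probably small. The illustrative range (11.0 to 19.0 points against a planned 15) rests on assumed rescue and success rates. It also assumes that every rescued child would otherwise have failed. That is most plausible after motor deterioration and less so after stereoacuity deterioration or an approved exception. The range should not be read as a forecast. Nor does the finding show that the observed-data analysis is wrong. It shows that results for these outcomes and for the primary mean may differ because of unequal rescue, with nothing planned to reveal it.

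**What to change.** At 12 and 18 months, add for the four outcomes an analysis aligned with the primary rule. Report it beside the observed-data version, and state which supplies the p-value, including the FDR-controlled p-values where the outcome is in that group.

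- **4.1.2:** derive 1- and 2-point improvement from the imputed mean distance control scores already produced under SAP 2.1.9.
- **4.1.1:** count children prescribed non-study treatment as not meeting the outcome.
- **4.1.5 and 4.1.6:** set values after non-study treatment to missing, and impute them from visits up to its prescription.
- **4.1.4:** say whether near control uses Section 2 imputation or Section 4 observed data.

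Simple carry-forward should not be the sole main rule.

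The cost is a short SAP paragraph and some extra runs. Barnard's test does not pool directly over 100 imputations, so the improvement proportions need a pooled difference and standard error. Imputed PACT and stereoacuity will rest on few visits, since 6 months is the only scheduled office visit between enrolment and 12 months. The 4.1.1 rule will class as failures some children who had good control when rescued. The 12-month visits were due by December 2019 and this SAP is dated February 2021, so the added analyses should be labelled as specified late.

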- Mean distance control (average of 3 measurements) will be compared between treatment groups using an analysis of covariance (ANCOVA) model, which adjusts for baseline distance control, distance PACT, age, refractive error, and use of ADHD medication, to address potential residual confounding.
- The proportion of subjects with no spontaneous tropia will be compared between treatment groups as in section 5.1.2.1.
- Axial length, flat corneal radius, anterior chamber depth, and lens thickness (if available) will be compared between treatment groups as in section 5.3.2.3 and
- Secondary outcomes of near control, angle magnitude, and near stereoacuity will also be compared between treatment groups as in section 5.3.1.
- Treatments used since the last visit will be tabulated by treatment group.

	PROTOCOL AMENDMENT I (11-8-16)
]	This amendment provides for the following protocol changes:
]	Protocol Change #1
r	Original Protocol At the time of enrollment and each follow-up visit at 6, 12, 15, and 18 months, parents are asked to respond to a survey of symptoms potentially associated with spectacle treatment (headaches, eye strain, and other problems with spectacle wear) based on their observations of their child in the past weeks.
(Changed Protocol
1	 To add a 7-question survey of intermittent exotropia symptoms to be administered to the child. To add a health-related quality of life questionnaire to evaluate whether either treatment impacts the effect of intermittent exotropia on quality of life.
	• Children ages 5 and older at the time of enrollment will complete an 11-item questionnaire to assess how their eye condition affects their quality of life. Children years of age and younger at the time of enrollment will not complete the child questionnaire.
	 A 16-item parental questionnaire will assess how the child's eye condition affects the quality of life of the parent (for all subjects).
3	3. The surveys and questionnaires will be completed at the time of enrollment; and at 6-month, 12-month, and 18-month follow-up visits.

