2.4 Testing at the Enrollment Visit

Initial testing at the enrollment visit should be performed without cycloplegia and with the subject's habitual correction (with spectacles if currently wearing, or without spectacles if not

currently wearing).* Trial frames should NOT be used for testing at the enrollment visit for any reason.

* The exception is a subject wearing spectacles not required by pre-randomization criteria (see section 2.2). This subject can be tested with or without these spectacles, provided visual acuity criteria are still met under the condition in which they are evaluated (see section 2.2).

 There is no specified "waiting" time that needs to occur between measurements, although testing must be performed in the following specified order at the enrollment visit, an exception being that distance visual acuity can be tested either at the start of the visit or at the end of the visit:

- 1. Spectacle Prescription Verification (Lensometry): Prior to performing the enrollment examination, the subject's pre-randomization spectacle correction (if worn) is to be verified using a lensometer.
- 2. Health-Related Quality of Life Questionnaire and Symptom Surveys:
 - A brief survey of symptoms that may be associated with overminus such as headaches, eye strain, and problems with spectacle wear will be administered to the parents of the subjects. Parents are asked to respond to the survey questions based on their observations of their child in the past 2 weeks.
 - A brief survey of intermittent exotropia symptoms will be administered to the child.
 - Health-related quality of life (HRQOL) will be assessed using the following two components of the Intermittent Exotropia Questionnaire (IXTQ). 26,27
 - 1. Child IXTQ: A child questionnaire for children ages 5 years or older to assess how the child feels about his/her eye condition. Children 4 years and younger at the time of enrollment will not complete the child questionnaire.
 - 2. Parent IXTQ: A parental questionnaire to assess how the child's eye condition affects the parent (in all children).

STEPS 3 through 9 must be performed in the specified order by the same study-certified examiner (pediatric ophthalmologist, pediatric optometrist, or certified orthoptist) on the same day.

- 3. Control of the Exodeviation #1:
 - Control of exodeviation will be assessed in the habitual correction at distance and near using a standardized IXT control scale (*see below*).²¹

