419 whether the incorrectly-assigned value matched the assignment that would have been
420 chosen if the correct record from the randomization schedule was used. The imputed
421 dataset specified in Section 2.1.9 will be used. The results will be compared to the
422 original analyses to assess if bias was introduced by including these 28 participants who
423 were included in in the primary analyses despite being incorrectly randomized.

424

425 **4.1.4 Near Control**

426 At the 12 and 18-month time points, near control will be evaluated similarly to the
427 distance control primary analysis (Section 2).

428

429 **4.1.5 Angle Magnitude by PACT**

430 At the 12- and 18-month time points, a two-sided treatment group comparison of
431 magnitude of the deviation by Prism Alternate Cover Test (PACT) will be performed
432 using an ANCOVA model which adjusts for baseline PACT. The treatment group
433 difference, 95% confidence interval and p value will be calculated. The analysis will be
434 completed separately for distance PACT and at near PACT.

435

436 **4.1.6 Stereoacuity**

437 At the 12 and 18-month time points, a two-sided treatment group comparison of near
438 stereoacuity (measured with the Preschool Randot Test) will be performed using an
439 ANCOVA model which adjusts for baseline stereoacuity. The treatment group difference,
440 95% confidence interval, and p value will be calculated.

441

442 **4.1.7 Axial Length Measurement**

443 At the 18-month time point, mean axial length measurement will be compared between
444 treatment groups using an ANOVA model. The treatment group difference and a 95%
445 confidence interval will be calculated. Adjustment for baseline is not possible given that
446 these measurements were added late in the study (with Protocol Amendment II) and
447 therefore not collected at baseline.

448

449 **4.1.8 Additional Ocular Biometric Parameters**

450 At the 18-month time point, mean flat corneal radius, anterior chamber depth, and lens
451 thickness will each be compared (if available) between treatment groups using an
452 ANOVA model. The treatment group difference and a 95% confidence interval will be
453 calculated. Adjustment for baseline is not possible given that these measurements were
454 added late in the study (with Protocol Amendment II) and therefore not collected at
455 baseline.

456

457 **4.1.9 Refractive Error**

458 At the 12- and 18-month time points, a two-sided treatment group comparison of

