459 spherical equivalent refractive error will be performed using an ANCOVA model which
460 adjusts for baseline refractive error and baseline age. The latter was added as a post-hoc
461 adjustment factor, as age is expected to be associated with refractive error at the 12-
462 month (and 18-month) time points. The treatment group difference, 95% confidence
463 interval, and p-value will be calculated. This analysis will be done combining refractive
464 error obtained by subjective refraction or retinoscopy and separately from refractive error
465 obtained by autorefraction.

466

467 **4.1.10 Quality of Life**

468 At both the 12-month and 18-month time points, a two-sided treatment group comparison
469 of the child, and each of the three parent scales in the IXTQ HRQOL (Quality of Life)
470 will be performed each using the Wilcoxon Rank Sum Test as it is expected that scores
471 will not be normally distributed and will have a substantial ceiling effect. The treatment
472 group difference, 95% confidence interval, and p value will be calculated for both the
473 Rasch-scored data¹ and for 0 to 100-scaled data. The reported p-value will be derived
474 from the analysis of Rasch-scaled data, while to aid in interpretation, the 0 to 100-scaled
475 data will be used when reporting the median values for each treatment group.

476

¹ Leske DA, Holmes JM, Melia M, on behalf of Pediatric Eye Disease Investigator Group. Evaluation of the Intermittent Exotropia Questionnaire using Rasch analysis. JAMA Ophthalmol 2015;133:461-5.

477 A potential secondary manuscript, to be detailed in a separate SAP, will describe quality
478 of life, IXT symptoms, and spectacle wear issues, the relationships among these, and
479 relationships between these and clinical measures.

480

481 **4.1.11 IXT Symptom Survey**

482 A 7-item survey of IXT-related symptoms will be completed by the child at the
483 enrollment, 6-month, 12-month, and 18-month outcome exams. For each IXT-specific
484 symptom, the child is asked how often it occurs, using the response choices of “never”

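### SAP 4.1.10 compares the four IXTQ scales without using the enrollment scores, which gives up some precision on secondary outcomes, by an amount the documents cannot fix

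*SAP*

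**What the plan says.** SAP 4.1.10 plans a two-sided comparison of the IXTQ child scale and each of three parent scales at 12 and 18 months, which "will be performed each using the Wilcoxon Rank Sum Test as it is expected that scores" "will not be normally distributed and will have a substantial ceiling effect". It names no covariate, stratification or change score. It also requires that the "group difference, 95% confidence interval, and p value will be calculated for both the" Rasch and 0 to 100 scores, without naming the estimator of the difference. The reported p-value comes from the Rasch score, and the 0 to 100 score supplies the medians.

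The same instruments are completed at baseline. Protocol Amendment I, Change #1: "The surveys and questionnaires will be completed at the time of enrollment; and at 6-month, 12-month, and 18-month follow-up visits". The child scale has an age limit (Protocol 2.4): "Children 4 years and younger at the time of enrollment will not complete the child questionnaire".

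Elsewhere in SAP 4.1 an outcome is adjusted for its own baseline value: angle magnitude in 4.1.5 ("using an ANCOVA model which adjusts for baseline PACT"), stereoacuity in 4.1.6 ("ANCOVA model which adjusts for baseline stereoacuity") and refractive error in 4.1.9 ("adjusts for baseline refractive error and baseline age. The latter was added as a post-hoc" factor). For axial length and biometry, SAP 4.1.7 and 4.1.8 explain that no baseline measurement exists.

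Under SAP 4 the IXTQ tests fall in the second of two outcome groups, with the false discovery rate held at 5% in each. SAP 4.1 repeats every 18-month analysis in the cohort prescribed weaning.

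**The concern.** The stated reason supports a rank method. It does not explain leaving out a baseline score that is in hand, because a rank method can adjust for baseline. Without adjustment, stable differences between children and between parents remain in the error term. A real quality-of-life effect is then harder to detect, in tests that also carry a multiplicity adjustment. Amendment I added these questionnaires because the investigators wanted to know how overminus affects quality of life, so sensitivity here has some value.

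**Working it through.** **Plan's own figure.** The documents state no sample size, power, effect, SD or correlation for the IXTQ, so there is nothing to reproduce for this outcome. The trial's size for distance control (Protocol 5.7.1) does reproduce: 2 × (1.960 + 1.282)² × 1.8² / 0.65² = 161.2, hence 162 per arm. The exact t-test gives 162.1, rounded up to the stated 163 per arm (326). That makes about 160 per arm a reasonable assumption for the parent scales.

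**Large-sample gain.** Adjusting for a baseline with correlation r multiplies the error variance by 1 − r² and the interval width by √(1 − r²).
- r = 0.25: 1 − 0.0625 = 0.9375; width × 0.968 (3% narrower).
- r = 0.47: 1 − 0.2209 = 0.7791; width × 0.883 (12% narrower).
- r = 0.7: 1 − 0.49 = 0.51; width × 0.714 (29% narrower).

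The first two values are the point estimate and upper 95% limit in Protocol 5.7.1 for distance control at 8 weeks, a different outcome over a shorter interval. The third is an assumption.

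**Does the gain survive ranking and a ceiling?** Simulation: bivariate normal baseline and follow-up scores with latent correlation r, both cut off at a ceiling; 160 per arm; shift 0.28 SD; two-sided 5%; 10,000 runs per cell. All inputs are assumed. Rank ANCOVA regresses the midrank of follow-up on treatment and the midrank of baseline. Power in percent, Wilcoxon / rank ANCOVA:

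| r | 25% at ceiling | 40% | 60% |
|---|---|---|---|
| 0 | 65.8 / 65.6 | 62.5 / 62.4 | 53.8 / 53.6 |
| 0.25 | 65.5 / 67.9 | 62.2 / 64.2 | 53.7 / 55.0 |
| 0.4 | 65.1 / 71.5 | 62.2 / 67.1 | 53.9 / 57.8 |
| 0.55 | 65.7 / 78.4 | 62.7 / 73.6 | 54.0 / 62.8 |
| 0.7 | 65.6 / 87.6 | 61.9 / 83.0 | 53.2 / 70.1 |

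A separate repeat gave gains of about 1 to 3 points at r = 0.25, 4 to 7 at 0.4 and 17 to 21 at 0.7. Differences of about a point from the table are simulation error. Type I error was about 4.5 to 5.5% for both tests.

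**Other effect sizes.** A 0.28 SD shift puts Wilcoxon power near the middle of its range, where gains are largest. At 0.1 or 0.5 SD the gain is roughly 0 to 1 points at r = 0.25 to 0.4 and at most about 7 at r = 0.7.

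**Child scale.** With an assumed 110 per arm and a 0.28 SD shift, the gains are about 1 to 2, 3 to 6, 8 to 12 and 15 to 23 points at r = 0.25, 0.4, 0.55 and 0.7.

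**After the false discovery rate step.** Benjamini-Hochberg at 5% over 4 scales × 2 visits = 8 tests (family assumed; 0.28 SD; between-scale correlation 0.4; 3,000 runs): Wilcoxon power is 33 to 52%, and the gains are about 2 to 3, 4 to 8, 9 to 17 and 20 to 31 points at the same four correlations. The multiplicity step does not remove the gain.

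**Interval.** A percentile bootstrap interval for the adjusted mean difference covered 93.9 to 95.2%. It was 1.5 to 2.5% narrower than the unadjusted interval at r = 0.25 and 20 to 26% narrower at r = 0.7. The Hodges-Lehmann estimate, the natural companion to the Wilcoxon test, was exactly 0 in 18 to 23% of runs at a 25% ceiling, 78 to 84% at 40% and all runs at 60%, so it is a poor choice here.

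**The case against.** The strongest reply is that this is a preference for efficiency. The Wilcoxon test is valid and no power target exists for the IXTQ. The only correlation in the documents is 0.25, for another outcome, and there the gain is 1 to 3 points at best. The large gains need both a mid-power effect and r near 0.7, above even the 0.47 limit for distance control. The ceiling that the SAP expects also shrinks the gain: at r = 0.4, from 6.4 points at a 25% ceiling to 3.9 at 60%. All of this stands and limits the size claimed.

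The comparison with other outcomes is not clean either. SAP 4.1.1 tests absence of spontaneous tropia by Barnard's test without adjustment, although baseline status is known. A reader might infer that the SAP always adjusts where a baseline exists; it does not. Nor is baseline IXTQ wholly unused: Protocol 5.4.4 describes change in scores by group, and SAP 4.1.10 mentions a possible quality-of-life manuscript under a separate SAP. Neither is an adjusted comparison, so the omission remains.

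Timing is a fair point. The SAP is dated February 2021, and the last 12-month visits were planned for December 2019, which puts 18-month visits around mid-2020. The documents do not say whether IXTQ results by arm had been seen. The fix allows for both cases.

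**Conclusion.** The point holds as a modest improvement in efficiency. An available baseline is left out of eight secondary comparisons without a reason that covers the omission. Adding it costs essentially no power if the correlation is zero and helps if the correlation is moderate or high. The likely gain cannot be narrowed further: it runs from nearly nothing (r = 0.25, or a small or large effect) to about 17 to 21 points (r = 0.7 with a 0.28 SD shift, 160 per arm, 25 to 60% at ceiling), all on assumed inputs.

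A reader might infer that the planned test is biased or that the quality-of-life comparison is underpowered. The documents support neither reading. Randomization protects the type I error of the unadjusted test, no IXTQ power was promised, and the primary analysis and sample size are unaffected.

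**What to change.** In SAP 4.1.10:

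- Take the reported p-value for each scale and visit from rank ANCOVA: the midrank of the follow-up Rasch score on treatment and the midrank of the baseline Rasch score. Impute a missing baseline by the overall baseline mean before ranking.
- Report a baseline-adjusted mean difference with a percentile bootstrap 95% interval, resampling within arm, on the Rasch and 0 to 100 scales.
- Apply the same model to the 18-month repeat in the weaning cohort required by SAP 4.1.
- Leave the false discovery rate step unchanged, keep the 0 to 100 medians for description, and keep the unadjusted Wilcoxon test as a sensitivity analysis.
- If IXTQ data by arm have already been seen, keep the Wilcoxon p-value as the reported one and add rank ANCOVA as a labelled post-hoc analysis, as SAP 4.1.9 did with baseline age.

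Cost: no new data. There are 4 × 2 = 8 model fits plus 4 for the weaning cohort, 12 in all, and 12 × 2 = 24 bootstrap intervals. Children enrolled before Amendment I would lack a baseline score, and the documents give no count; if 10% do (assumed), mean imputation costs 0 to 3 power points. The rank p-value and the score-scale interval can disagree on significance, in 7 to 24% of simulated runs. Pairing a Wilcoxon p-value with an unadjusted mean-difference interval, an estimator the SAP does not specify, gave 10 to 19%, so most of the mismatch does not come from the change.
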